9 SAFETY EVALUATIONS

9.1 OVERVIEW OF SAFETY ANALYSIS METHODS

9.2 ADVERSE EVENTS AND UNANTICIPATED ADVERSE DEVICE EFFECTS

An AE is any undesired clinical response or complication experienced by a subject.

An unanticipated adverse device effect (UADE) is any serious adverse effect on health or safety, any life-threatening problem or death caused by, or associated with a device, if that effect, problem, or death was not previously identified in nature, severity, or degree of incidence in the clinical investigational plan or risk analysis; or any other unanticipated serious problem associated with a device that relates to the rights, safety, or welfare of subjects.

AEs and UADEs are classified into categories based on Common Terminology Criteria for Adverse Events (CTCAE) and collected as such on the CRFs. All recorded AEs will be listed and summarized.

For evaluation of causal relatedness to device or procedure, the categories are unrelated, possibly related, probably related, or definitely related.

For evaluation of event severity terms, the criteria are

- Grade 1: Mild; asymptomatic or mild symptoms; clinical or diagnostic observations only; intervention not indicated;
- Grade 2: Moderate; minimal, local or non-invasive intervention indicated; limiting age appropriate instrumental Activities of Daily Living;
- Grade 3: Severe or medically significant but not immediately life-threatening; hospitalization or prolongation of hospitalization indicated; disabling; limiting self-care Activities of Daily Living;
- Grade 4: Life-threatening consequences; urgent intervention indicated,
- Grade 5: Death related to AE

An overall summary will be prepared giving for frequency and percentages by treatment group and overall, for the number of subjects with at least one TEAE, TEAE related to study device, TEAE related to study procedure, serious adverse event (SAE), UADE, SAE related to study device, SAE related to study procedure, and TEAEs resulting in death.

The frequency and percentages of subjects with AEs will be summarized overall and for CTCAE. These summaries will be given overall and by treatment in separate tables for each of the following AE event sets:

All events

- Serious events
- UADEs
- Events by maximum severity
- Events by maximum relationship to study device
- Events by maximum relationship to study procedure
- Serious events by maximum severity
- Serious events by maximum relationship to study device
- Serious events by maximum relationship to study procedure

If a given subject experiences an AE with the same CTCAE more than once, the subject will be counted only once for the CTCAE at the greatest severity (i.e., mild, moderate, severe, life threatening, or death) and causality (i.e., attribution to study material).

For the tables classified by severity grade and relationship, if a patient has multiple occurrences of a AE with the same CTCAE, the event with the highest severity or closest relationship will be counted.

No imputation is planned for missing safety data.

In addition to a listing of all AE, a listing will be provided for AE narrativesI. Clinical Laboratory Evaluations

Clinical laboratory evaluations include urinalysis for pH and infection result and serum creatinine (mg/dL). All clinical laboratory evaluations will be presented in a by-subject listing.

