	clinically significant serious adverse events, both for each treatment group individually,
	and for the difference in the rates between the two treatment groups.
Primary Efficacy	Treatment success is defined as the proportion of study subjects who have a complete
Endpoint:	absence of stones or have residual fragments measuring ≤ 2 mm on the treatment side,
	as assessed by CT imaging through 30-day follow-up post index procedure.
	The primary efficacy endpoint will demonstrate that the investigational arm (Acoustic
	Enhancer with URS-LL) is superior in the fragmentation of stones to ≤ 2mm versus the
	control arm (URS-LL).
Secondary Efficacy	Total radiant energy (TRE): Mean value of laser energy, measured for each subject in
Endpoint:	kilojoules divided by the stone cross-sectional area. The secondary endpoint will
	demonstrate non-inferiority of the mean TRE used between the investigational arm and
	the control arm.
Additional	Mean total lasering time
Observations:	 Additional interventional stone procedures for stone(s) that were treated as part of
	the AEROLITH study.
	• Adverse Events by type, over time, severity, seriousness, and relatedness. AEs will be
	tabulated and summarized as counts and percentages. AEs will also be cross
	tabulated according to:
	- Severity
	- Unanticipated Adverse Device Effect (UADE)
	 Seriousness (Serious Adverse Event (SAE), Non-serious AE) Device Relatedness (Uprelated Ressibly Related Probably Related
	 Device-Relatedness (Unrelated, Possibly Related, Probably Related, Definitely Related)
	 Procedure-Relatedness (Unrelated, Possibly Related, Probably
	Related, Definitely Related)
Statistical Analyses	A sample size of 196 subjects randomized 1:1 to the investigational arm (Acoustic
/ Sample Size	Enhancer with URS-LL) and the control arm (URS-LL) was selected based on consideration
	of the primary endpoint. Assuming no more than 10% non-evaluable subjects, this

Justification:	provides a randomized sample size of 176 subjects (88 per arm).	
Justification.	The primary hypothesis test for the treatment success outcome is as follows:	
	The printing hypothesis test for the treatment success outcome is as follows.	
	H ₀ : $p_{AE} \le p_{Control}$ vs H ₁ : $p_{AE} > p_{Control}$	

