6.4. Additional Observations

- 6.4.1. Mean total lasering time. While total radiant energy is a more rigorous and broadly applicable indicator of improved stone erosion, pitting and fragmentation through the generation of additional stone-fragmenting shockwaves, a demonstration of lower mean lasering time in the Acoustic Enhancer arm compared to the standard laser arm could be clinically important.
- 6.4.2. Additional interventional stone procedure(s) on stone(s) that were treated as part of the AEROLITH study.
- 6.4.3. Adverse Events (AEs) by type over time, severity, seriousness, and relatedness. AEs will be tabulated and summarized as counts and percentages. AEs will also be cross tabulated according to:
 - Severity
 - Unanticipated Adverse Device Effect (UADE)
 - Seriousness (Serious Adverse Event (SAE), Non-serious AE)
 - Device-Relatedness (Unrelated, Possibly Related, Probably Related, Definitely Related)
 - Procedure-Relatedness (Unrelated, Possibly Related, Probably Related, Definitely Related)

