*CT within 60 days of subject signing consent. If CT imaging has not been conducted yet for the patient, please follow CT image acquisition parameters detailed in CLIN-0002.

Stone measurement will follow the Radiographic Evaluation Protocol of Applaud Medical's Acoustic Enhancer with Laser Lithotripsy System in the Urinary Treatment of Stones (Doc. No. CLIN-0003)

⁺ Pregnancy test to be done on the day of treatment prior to randomization

** See Imaging Acquisition Protocol, Acoustic Enhancer Research in Laser Lithotripsy (Doc. No. CLIN-0002)

***Only those subjects who have unresolved hydronephrosis at 30 days post-procedure.

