11.1. Adverse Event

An adverse event (AE) is any undesired clinical response or complication experienced by a subject. Monitoring and documenting of adverse events will begin at the start of the index procedure. When an adverse event is recorded as ongoing, an effort will be made to follow-up on the event at subsequent subject visits until the event is resolved or the subject exits the study.

CONFIDENTIAL Page 36 of 53

In this study, adverse events should be reported beginning at the time of administration of general anesthesia for the index procedure. Pre-existing conditions (recorded on the Medical History CRF), which occur during the study at the same severity as in the subject's history, should not be recorded as adverse events. Pre-existing conditions (recorded on the Medical History CRF) that worsen during the study OR a new episode begins must be recorded as AE(s). The onset date should be the start of the current episode or the date of the change in severity, not the onset date recorded on the Medical History CRF.

Upon enrollment, if a new adverse event is reported and subsequently determined to be medical history not previously documented, the information should be added to the medical history CRF. The event should be recorded as an AE only if there was a change in severity.

Intermittent Events

An AE that occurs intermittently at the same severity should be aggregated and recorded as one event unless, in the opinion of the Investigator, the events should be reported as discrete events (medical diagnosis terms).

- The onset date is the start of the first episode during the study.
- The resolution date is the end of the last episode (or may be persistent, if ongoing at the end of the study).
- The site should record "intermittent" in the AE description. If an intermittent event meets the regulatory criteria for seriousness, the associated frequency of the adverse event term (e.g., 4x/week) should be captured in the narrative/comment section of the CRF.
- If the event changes in severity or relationship to study device, it should be recorded as an AE update.

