13 CHANGES TO THE ANALYSES PLANNED IN THE PROTOCOL

In the protocol it is stated that the total number of secondary stone treatments will be summarized and a Cochran-Armitage trend test will be used to evaluate the null hypothesis that there is no trend in the number of stones between the groups. This was removed from the SAP. Because subjects exit the study 30 days after receiving treatment, this data is unlikely to be available.

No further changes exist between the protocol-defined statistical analyses and those presented in this statistical plan.

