14 TABLES OF CONTENTS FOR APPENDICES

14.1 TABLES

Table Number	Population	Title
14.0.1	Randomized	Subject Disposition
14.0.2	Randomized	Summary of Subjects Excluded from Analyses
14.0.3	ITT	Subject Accounting
14.0.4	ITT	Major Protocol Deviations
14.1.1.1	ITT	Summary of Subject Demographics
14.1.1.2	PP	Summary of Subject Demographics
14.1.1.3	Safety	Summary of Subject Demographics
14.1.2.1	ITT	Summary of Baseline Characteristics
14.1.2.2	PP	Summary of Baseline Characteristics
14.1.2.3	Safety	Summary of Baseline Characteristics
14.1.3.1	Safety	Prior Medications by ATC Class and Preferred Term
14.1.3.2	Safety	Prior Kidney Stone Medications by ATC Class and Preferred Term
14.1.3.3	Safety	Prior Medications of Interest by ATC Class and Preferred Term
14.1.3.4	Safety	Concomitant Medications by ATC Class and Preferred Term
14.1.3.5	Safety	Concomitant Kidney Stone Medications by ATC Class and Preferred Term
14.1.3.6	Safety	Concomitant Medications of Interest by ATC Class and Preferred Term
14.1.4.1	ITT	Summary of Study Procedure
14.1.4.2	ITT	Summary of Study Procedure: Lyophilized Acoustic Enhancer
14.2.1	ITT	Analysis of Total Lasering Time
14.2.2	ITT	Analysis of Interventional Stone Procedures
14.2.3.1	ITT	Summary of Subjects Receiving Pain Medication for Kidney Stones
14.2.3.2	PP	Summary of Subjects Receiving Pain Medication for Kidney Stones
14.3.1.1	Safety	Overview of Treatment Emergent Adverse Events
14.3.2.1.1	Safety	Summary of Treatment Emergent Adverse Events

	1	
14.3.2.1.2	Safety	Summary of Treatment Emergent Adverse Events by Severity
14.3.2.1.3	Safety	Summary of Adverse Events by Relationship to Device
14.3.2.1.4	Safety	Summary of Adverse Events by Relationship to Procedure
14.3.2.1.5	Safety	Summary of Unanticipated Device-Related Treatment Emergent Adverse Events
14.3.2.2.1	Safety	Summary of Serious Treatment Emergent Adverse Events
14.3.2.2.2	Safety	Summary of Serious Treatment Emergent Adverse Events by Severity
14.3.2.2.3	Safety	Summary of Serious Treatment Emergent Adverse Events by Relationship to Device
14.3.2.2.4	Safety	Summary of Serious Treatment Emergent Adverse Events by Relationship to Procedure
14.3.3.1	Safety	Summary of Vital Signs

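### The protocol plans adverse events over time, but the SAP has no such summary, and its whole-study percentages mix common follow-up with late events sought only in an outcome-selected subset

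*SAP*

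**What the plan says.** Protocol 6.4.3 lists among the additional observations "Adverse Events (AEs) by type over time, severity, seriousness, and relatedness". The Additional Observations row of the synopsis makes the same commitment. Both add counts and percentages, and cross-tabulation by severity, UADE, seriousness, device-relatedness and procedure-relatedness.

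SAP 9.2 introduces its tables with "These summaries will be given overall and by treatment in separate tables for each of the following AE event sets". Nine sets follow: all events, serious events, UADEs, three by maximum severity or relationship, and the same three for serious events. For repeated events in a category, "the subject will be counted only once for the CTCAE at the greatest severity". SAP 5 sets the default percentage denominator as all subjects of the treatment group in the population concerned.

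SAP 13 reports one departure from the protocol, a dropped Cochran-Armitage test, and then states: "No further changes exist between the protocol-defined statistical analyses and those presented in this statistical plan".

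On follow-up, Protocol 11.1 says that "adverse events should be reported beginning at the time of administration of general anesthesia for the index procedure". Routine exit is at the 30-day visit, with a window of +14 days (Protocol 8.5). The footnote to Table 2 of the protocol limits the Day 90 visit: "Only those subjects who have unresolved hydronephrosis at 30 days post-procedure". Protocol 5.6 and 8.6 define the qualifying hydronephrosis more fully, and 5.6 adds that subjects with unresolved device- or procedure-related SAEs at 30 days are followed until resolution or stability.

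**The concern.** There are two linked problems. First, a summary that the protocol states in two places is missing from the SAP, and the SAP section meant to record departures says there are no others.

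Second, the missing time dimension is what would make the AE percentages readable. The period over which events are sought is not the same for everyone, and who is followed longer depends on what happened after treatment. If the arms differ in hydronephrosis or in unresolved related SAEs, they also differ in how long other events are looked for. A whole-study percentage on a whole-arm denominator cannot separate a difference in event rate from a difference in time under observation.

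The AE tables carry weight here. Study success (Protocol 6.6) depends on safety findings being offset by benefit, and SAP 12 plans no data safety and monitoring board.

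**Working it through.** The plan states no figure on this point, so the check is first a comparison of texts.

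| Item | Protocol | SAP |
|---|---|---|
| Type, severity, seriousness, relatedness, UADE | Synopsis, 6.4.3 | Present in 9.2 and 14.1 |
| Over time | Synopsis, 6.4.3 | Absent from all nine sets in 9.2 |
| AE tables | None specified | 14.3.1.1, 14.3.2.1.1 to 14.3.2.1.5 and 14.3.2.2.1 to 14.3.2.2.4: none by onset, visit or time since procedure (typical title: "Summary of Treatment Emergent Adverse Events by Severity") |
| Figures | None specified | None planned (14.2) |
| Declared change | Not applicable | Cochran-Armitage test only (13) |

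The SAP does use time for other data: medications by timing in 6.4.4, and vital signs by time point in 9.3.

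**Who is observed, and when**

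1. Scheduled common follow-up runs from anesthesia to the Day 30 visit, that is 30 to 30 + 14 = 44 days.
2. Subjects with qualifying hydronephrosis continue to 90 ± 21 days, that is 69 to 111 days. At that visit any reported AE is documented, not only hydronephrosis (Protocol 8.6).
3. Subjects with an unresolved related SAE at Day 30 are followed for as long as that takes to resolve or stabilize. No fixed length is set.
4. Events from all three groups enter the same row, once per subject and category, over the full arm.

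**Size**

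The documents give neither the share followed to Day 90 nor a late-event risk, so both inputs below are assumptions. Let f be the share of a 98-subject arm followed to Day 90, and r the share of those with a late AE. The contribution to the arm's percentage is f × r.

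| f | Subjects, 98 × f | r = 0.20 | r = 0.50 |
|---|---|---|---|
| 0.05 | 4.9 | 1.0% | 2.5% |
| 0.10 | 9.8 | 2.0% | 5.0% |
| 0.20 | 19.6 | 4.0% | 10.0% |

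If one arm had f = 0.05 and the other f = 0.20 with the same r, the gap would be 4.0% − 1.0% = 3.0 points at r = 0.20, and 10.0% − 2.5% = 7.5 points at r = 0.50. A difference in hydronephrosis could itself be a true treatment effect. The gap in other event types would arise because one arm was watched longer.

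These values are ceilings for any one row. Here r covers all event types together, and a subject already counted in a row is not counted again. In particular, new, worsened or recurred hydronephrosis is itself recordable as an AE (Protocol 11.1), so those subjects should already be in the any-AE row. The mixing therefore bears on category rows, on maximum severity and relationship, and on SAE rows where the hydronephrosis was not serious.

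**The case against.** The strongest reply is that nothing defined has been dropped. The protocol's cross-tabulation list does not include time, section 10 of the protocol gives no method for it, and the SAP delivers every item on that list. On a narrow reading of what a protocol-defined statistical analysis is, SAP 13 may be literally correct. This carries some weight, but a summary stated in both the synopsis and 6.4.3 should be produced or its removal declared.

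A reader might go further and infer that the planned tables would hide an acute reaction to the device. The documents do not support that. SAP 9.2 summarizes by CTCAE category, so an allergic reaction or a urinary tract rupture has its own row. Tables 14.3.2.1.3 and 14.3.2.2.3 show relationship to device, and listings 16.2.7.1 to 16.2.7.3 remain. Protocol 9.1 puts the listed device-material risks at no more than 0.01% of subjects, or 98 × 0.0001 = about 0.01 expected events per arm. The protocol also does not state when these risks would appear. One qualification remains: relatedness is the investigator's judgment (Protocol 11.1), and the blinding described in Protocol 7.4 covers subjects and the CT reader only. Onset date does not depend on that judgment.

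Nor should a reader infer that everyone with an unresolved related SAE is followed to about Day 90. Protocol 5.6 sets resolution or stability as the end, which could come soon after Day 30.

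Finally, onset up to the Day 30 visit is not one fixed length: it spans 30 to 44 days, and less after dropout. That is correct. It is the scheduled common period, and its length does not depend by design on hydronephrosis or an SAE.

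**Conclusion.** The point holds as a gap between the documents with a modest analytic consequence. The protocol plans AEs over time, the SAP has no such summary, and SAP 13 does not say so. The planned percentages pool the scheduled common follow-up with late events ascertained only in subjects selected on a post-treatment outcome.

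The effect cannot be sized from the documents. The 1.0 to 10.0 point range rests wholly on the assumed 5% to 20% followed and 20% to 50% with late events, and it is a ceiling. Onset dates are collected, so nothing is lost from the data, only from the summaries. The primary effectiveness result is not affected. The change should be made because it delivers a stated commitment and removes an avoidable ambiguity at very little cost.

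**What to change.** 1. Add to SAP 9.2 and 14.1 one table for all AEs and one for SAEs, by arm and onset interval: procedure day; after the procedure day to Day 14; Day 15 to the Day 30 visit; and after the Day 30 visit, with the number still followed as the denominator in the last interval.
2. Base the general between-arm comparison of AEs and SAEs on onset up to the Day 30 visit. Leave the primary safety endpoint, which runs through 90 days, as it is.
3. Use one definition of the procedure day. SAP 2 and 4.1 call it Day 1 and SAP 5 calls it Day 0; the intervals are ambiguous until this is settled.
4. Correct SAP 13 so that it agrees with what the SAP delivers.

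The cost is two extra descriptive tables and some SAP wording. Onset dates are already collected under Protocol 11.1, so no new data are needed.

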8. SUBJECT ASSESSMENT AND STUDY VISIT SCHEDULE AND PROCEDURES

8.1. Pre-Treatment Visit

After the subject has completed the informed consent process, research staff will review potential subject's medical history, including available images, to verify study subject's eligibility. In addition, research staff will conduct protocol required assessments prior to the index procedure to obtain baseline information and verify subject eligibility.

- As part of routine care, study subjects may be prescribed medications such as analgesics, alpha blockers, calcium channel blockers, antibiotics to take as needed.
- Research staff will review subject's medical history, including available images, to verify study eligibility.
- Subjects will complete a baseline health status and undergo focused urogenital calculus physical exam and vital signs.

- Subjects will undergo a CT scan to measure stone dimensions (in mm), and location (e.g., the upper (superior) pole, lower (inferior) pole, and interpolar region of the kidney, pelvis of the kidney, and proximal ureter). This will be noted on the Electronic Case Report Form (eCRF). If there are multiple stones, each one will need to be measured and its location (i.e., pelvis, ureter), size will be documented.
 - CT image acquisition parameters will follow CLIN-0002: Image Acquisition Protocol, AEROLITH Study. A CT image collected prior to screening may be used as baseline CT image. The CT image will be used to measure stone size and the location of the stone.
 - Measuring baseline stone size(s) will be conducted by the investigator following CLIN- 0003: Radiographic Evaluation Protocol of Applaud's Acoustic Enhancer with Laser Lithotripsy System in the Treatment of Urinary Stones
 - A Stone Size Measurement Verification Electronic Case Report Form (eCRF) will be completed by the investigational site and the baseline CT image will be uploaded to the core lab for analysis following CLIN-0003.
- Subjects will undergo a urinalysis to verify absence of Urinary Tract Infection (UTI) and verify pH level is ≥ 5.5. *Note:* If a patient's largest stone intensity is ≥ 500HU and has a historical pH value of ≥ 5.5, a recently tested (within 30 days of consent) urine pH showing <5.5 in this case is acceptable.
- Serum creatinine to verify renal function and serum creatinine is < 1.5mg/dl.

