8.5. 30-day follow-up (30 +14 days after procedure)

- Conduct focused urogenital calculus physical exam and vital signs.
- Measure serum creatinine to assess renal function.
- Document any reported AEs since last visit (see Adverse Events section below)
- If symptoms of Urinary Tract Infection (UTI) are reported by subjects, conduct a urinalysis and subsequent urine culture if clinically indicated to verify presence/absence of UTI.
- Document all prescription medications. In addition, document any non-prescription medication that may impact stone disease, acting as stone formation promoters (e.g., calcium or ascorbic acid) or stone formation inhibitors (e.g., magnesium or citric acid)
- Conduct CT imaging following acquisition parameters delineated in CLIN-0002: Image Acquisition Protocol, AEROLITH Study
 - **Note 1:** As presence of ureteral stents may obscure image analysis, remove stents from the treated kidney/ureter prior to collecting the CT images.
 - **Note 2:** If a stent is removed outside of the window (3-14 days post procedure), this will be captured and documented using Protocol Deviation CRF as minor protocol deviation.
 - Note 3: If a stent is removed at >14 days, verify absence or presence of calcification and/or encrustation via standard of care imaging (e.g., KUB X-ray). If calcification and/or encrustation is observed, complete Adverse Event CRF.
- Upload the CT images to the core lab for analysis.
- Complete Study Exit CRF
 - **Note 1:** For those subjects with new or on-going device and/or procedure-related serious adverse events at 30 days post procedure, they will be followed until the event has resolved or is deemed stable by the investigator.
 - **Note 2:** For those subjects with new or on-going device and/or procedure related hydronephrosis and those subjects with pre-existing (prior to treatment) hydronephrosis that have worsened or recurred since baseline, they will be followed through 90-days post procedure (see below).

8.6. 90-day follow-up and Study exit (90 +/- 21 days after last treatment) only for those subjects with new and unresolved device and/or procedure related hydronephrosis and subjects with pre-existing (prior to treatment) hydronephrosis that have worsened or recurred at 30 days

- Conduct focused urogenital calculus physical exam and vital signs.
- Document any reported AEs since last visit (see Adverse Events section below).

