10. STATISTICAL METHODS

10.1. General Considerations

The study results will be reported using descriptive summaries and data will be made available in listings or electronic format as required. The data will be summarized according to randomized treatment group (investigational arm and control arm). Inferential analyses will be performed for the primary endpoints and other endpoints as outlined below. For continuous variables, descriptive statistics will include means, standard deviations, medians and ranges. Categorical variables will be summarized in frequency distributions and reported with the count and percentages. Percentages will be calculated based on observed values. Except for the primary effectiveness endpoint analyses, a two-sided p-value less than or equal 0.05 will be considered statistically significant. The primary effectiveness analyses p-values associated with statistical significance are outlined below. Where reported, all confidence intervals will be two-sided 95% CIs.

A separate Statistical Analysis Plan will be constructed with additional detail on statistical considerations and content of tables, listing and figures from the various data analyses. Statistical analyses will be performed using SAS (version 9.4 or higher, SAS Institute Inc. Cary, NC), R (version 3.0 or higher, R Foundation for Statistical Computing, Vienna, Austria) or other widely accepted statistical or graphical software.

Results will additionally be stratified according to stone location (the upper (superior) pole, lower (inferior) pole, and interpolar region of the kidney, pelvis of the kidney, and proximal ureter) and stone diameter (< median, > median where the median is based on all ITT subjects).

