9.3 VITAL SIGNS

Vital signs results including blood pressure (systolic and diastolic; mmHg), pulse rate (beats per minute), and body temperature (C) will be listed for individual subjects.

Baseline for vital signs measurements will be defined as the last evaluation before dosing with study medication. Summary statistics, including change from baseline, will be determined for each measure and will be summarized overall by treatment and time point using the Safety population.

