14.3 LISTINGS

Listing Number	Population	Title
16.1.7	All Subjects	Randomization Scheme
16.2.1.1	Randomized	Subject Disposition
16.2.1.2	Randomized	Discontinued Subjects
16.2.1.3	Screen Failures	Screen Failures
16.2.2.1	All Subjects	Subject Inclusion / Exclusion Criteria
16.2.3.1	All Subjects	Analysis Populations
16.2.3.2	Enrolled	Major Protocol Deviations
16.2.4.1	Enrolled	Subject Demographics and Baseline Information
16.2.4.2.1	Enrolled	Urinary Stone History
16.2.4.2.2	Enrolled	Stone Location
16.2.4.3	Enrolled	General Medical History
16.2.4.4	Safety	Prior and Concomitant Medications
16.2.5.1	Safety	Procedure Details – Part 1
16.2.5.2	Safety	Procedure Details – Part 2

16.2.5.3	Safety	Procedure Details – Part 3
16.2.7.1	Safety	Adverse Events
16.2.7.2	Safety	Adverse Event Narratives
16.2.7.3	Safety	Serious Adverse Events
16.2.8.1	Safety	Laboratory Assessments
16.2.8.2	Safety	Urine Pregnancy Tests
16.2.8.3	Safety	Vital Signs
16.2.8.4	Safety	Focused Urogenital Calculus Physical Exam

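### Serum creatinine is measured before and after treatment, but the SAP only lists it by subject, so its change from baseline is never summarised or compared by arm

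*SAP*

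**What the plan says.** Protocol 8.1 includes creatinine in the pre-treatment work-up: "Serum creatinine to verify renal function and serum creatinine is < 1.5mg/dl". Protocol 8.5 repeats it at the 30-day visit: "Measure serum creatinine to assess renal function". Table 2 of the protocol marks it at those two visits and not at Day 90. Urinalysis and the pregnancy test are the only other laboratory tests in that table, so creatinine is the only one that addresses renal function.

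The SAP deals with laboratory data in a short paragraph at the end of section 9.2. It names urinalysis and serum creatinine and then states the whole reporting plan: "All clinical laboratory evaluations will be presented in a by-subject listing". The listing index in SAP 14.3 has the matching entry, 16.2.8.1, titled "Laboratory Assessments". The table index in SAP 14.1 has no laboratory entry; its last safety table is 14.3.3.1, for vital signs.

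Vital signs are treated differently. SAP 9.3 says: "Summary statistics, including change from baseline, will be determined for each measure", by treatment and time point, in the Safety population.

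The general rule in Protocol 10.1 is that data are summarised by randomised arm, and "For continuous variables, descriptive statistics will include means, standard deviations, medians and ranges". SAP section 5 likewise provides for summaries of continuous data and defines change from baseline. SAP section 13 drops one trend test and then says: "No further changes exist between the protocol-defined statistical analyses and those presented in this statistical plan".

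**The concern.** The trial places a new material in the urinary collecting system, and the protocol gives assessment of renal function as the reason for the Day 30 creatinine. Protocol 9.1 lists kidney injury, together with infection needing treatment, among the occasional risks of ureteroscopic laser lithotripsy (2% to 10% of subjects). Protocol 6.6 makes study success depend on weighing safety findings against benefit.

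A modest average rise in one arm, or a few more subjects with raised values, is the kind of finding that a by-arm summary shows and a listing hides. Under this SAP it would be seen by arm only if investigators reported the individual changes as adverse events. Otherwise a reader would have to compare arms by eye, over as many as 196 subjects with two scheduled values each (196 × 2 = 392 values).

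**Working it through.** **1. Planned outputs that contain creatinine.** This count comes from SAP 9.2, 14.1, 14.2 and 14.3.

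| Output type | Number with creatinine |
|---|---|
| Summary tables | 0 |
| Figures | 0 (none are planned at all) |
| Listings | 1 (16.2.8.1) |

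**2. Whether another document fills the gap.** SAP sections 4 and 8 refer to a separate analysis plan, which is not among the documents. They describe it as covering the primary and secondary endpoints. Protocol 6.1 to 6.4 and 10.8 do not name creatinine as an endpoint or an additional observation, so there is no reason to expect it there.

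**3. Comparison with vital signs.** Both are taken at screening and Day 30.

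| | Vital signs | Serum creatinine |
|---|---|---|
| Screening and Day 30 values | Yes | Yes |
| Summary by arm | Yes (SAP 9.3) | No |
| Change from baseline by arm | Yes (Table 14.3.3.1) | No |
| Subject listing | Yes (16.2.8.3) | Yes (16.2.8.1) |

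The SAP gives no reason for the difference.

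**4. The plan's own sample size.** This supplies the number per arm. The documents give no figure for creatinine.
- Inputs (Protocol 10.3, SAP section 3): 55% versus 75%, one-sided 0.025, 88 evaluable per arm, 10% non-evaluable.
- Power with 88 per arm, pooled variance under the null: 0.7996, which reproduces the stated 80%.
- Inflation: 176 / (1 − 0.10) = 195.6, rounded up to 196, as stated.

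**5. Precision of a by-arm creatinine comparison.** The 95% CI half-width for the between-arm difference in mean change is 1.96 × SD × √(2/n), where SD is that of the change from screening to Day 30.
- n = 88: 1.96 × √(2/88) = 0.295, so 0.295 SD.
- n = 98 (all randomised subjects with both values): 1.96 × √(2/98) = 0.280, so 0.280 SD.

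The documents give no SD of change, so the values below are assumptions:

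| Assumed SD (mg/dl) | Half-width, n = 88 (mg/dl) |
|---|---|
| 0.15 | 0.295 × 0.15 = 0.044 |
| 0.20 | 0.295 × 0.20 = 0.059 |
| 0.30 | 0.295 × 0.30 = 0.089 |

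The figure of 88 is the efficacy-evaluable number, used here as a stand-in for subjects with both creatinine values. The Safety population could supply somewhat more or fewer pairs.

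**The case against.** The strongest reply is that renal safety is covered elsewhere. Adverse events are tabulated by treatment, CTCAE category, severity and relatedness (SAP 9.2). Protocol 6.1 provides confidence intervals for the between-arm difference in serious infection, including pyelonephritis, and in new stricture needing surgery. Protocol 11.1 implies that a worsened laboratory value can be an adverse event, and Grade 1 extends to findings that are only diagnostic. Hydronephrosis is followed to 90 days, and Protocol section 13 has a medical monitor review safety data for trends.

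Most of this stands. It rules out the broader reading, which a reader might infer, that renal safety is never compared between arms. It does not dispose of the narrower point. The adverse event route depends on investigators choosing to report, and the protocol sets no creatinine threshold for doing so. The primary safety endpoint concerns infection and stricture, not renal function. SAP 9.5 plans no reports of the imaging data, and the medical monitor's review has no specified by-arm output.

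A second reply is that Protocol 10.1 also allows data to be made available in listings, and that the protocol prescribes no creatinine-specific analysis. That also stands. A reader might take the closing statement of SAP section 13 as a false declaration; the documents do not go that far. The listing-only rule fits poorly with the general by-arm sentence in Protocol 10.1, but it removes no analysis that the protocol specifically defined.

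Third, the half-width in mg/dl rests on unsourced SDs, and the documents give no clinically relevant difference to set it against. This is correct. The figures show that a usable interval could be calculated; they do not show harm.

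**Conclusion.** The point holds in a limited form. Creatinine change from baseline is not summarised or compared by arm in any planned output. Only investigator-reported renal adverse events, and the infection and stricture rates, are. This is a gap in descriptive safety reporting. It does not touch the primary analysis, type I error, sample size or data collection. The change is worth making because it costs almost nothing and safety has to be weighed against benefit.

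The firm statement of size is a half-width of about 0.295 SD with 88 subjects per arm. The range of 0.04 to 0.09 mg/dl holds only if the SD of change lies between 0.15 and 0.30 mg/dl.

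A reader might also link this to the eligibility wording: Protocol 5.8.18 excludes values above 1.5 mg/dl, while 8.1 requires values below 1.5 mg/dl, so a value of exactly 1.5 passes one and fails the other. Those two places must be reconciled, but that is a separate matter. Under either wording an eligible subject starts no higher than 1.5, so a count of Day 30 values above 1.5 is well defined.

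**What to change.** In SAP 9.2, replace the listing-only sentence with a listing plus one table, and add that table to SAP 14.1. It should use the Safety population by actual treatment and show:
- creatinine at baseline and Day 30, and change from baseline, with the standard descriptive statistics and the number of subjects with both values;
- the between-arm difference in mean change with a two-sided 95% CI, labelled descriptive and without a hypothesis test;
- the number and percentage in each arm with a Day 30 value above 1.5 mg/dl, with a note that this is the eligibility limit, used only as a descriptive reference and not as a safety threshold.

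The cost is one more safety table. No new samples, visits or alpha are needed. It should be added before database lock and unblinding, because SAP section 1 would label the same table post hoc if it were produced afterwards.
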